#### 7.10.13.7 CCR5 Receptor Occupancy

- To assess the number CCR5 receptors on patients' CD4 cell surface. Of those CCR5 receptors, the test will also assess the number and percentage of CCR5 receptors that are covered by PRO 140.
- Frequency of testing: At T1, T2, T4, T6, T8, T10, T12, T14, T16, T17, and at least once every four weeks between T18-21, T22-25, T26-29, T30-33, T34-37, T38-41, T42-45, (when subject comes to clinic), at T48, and VF visits.

- Samples will be shipped overnight to InCellDx Lab. No samples should be collected on Fridays due to InCellDx Lab being closed Saturdays.

#### **7.10.13.8 CCR5 Genotyping**

- To correlate the CCR5 homozygous or heterozygous status with virologic response to PRO 140 reported during the treatment phase.
- No new sample collection is needed. The residual whole blood sample collected for tropism assessment at Screening or at post-treatment visits will be used for testing of CCR5 genotyping (homozygous or heterozygous status).

#### **7.10.14 Urinalysis**

- Frequency of testing: At the Screening Visit (SV), T12, T22-25, T34-37, T48 or VF visit
- Urine samples will be tested for color, appearance, specific gravity, pH, protein, glucose, occult blood, ketones, leukocyte esterase, nitrite, bilirubin, urobilinogen, and microscopic examination of urine sediment

#### **7.10.15 CSF sample collection for CNS sub-study**

- Frequency of testing: At the T1 (prior to first dose of PRO 140), T4 and VF visits.
- In a subset of participants (n=20) to assess the extent of PRO 140 entry into the CNS compartment, and to evaluate virologic responses in CSF.

#### **7.10.16 Genital Secretion sample collection for GU sub-study**

- Frequency of testing: At the T1 (prior to first dose of PRO 140), T4, T16 and VF visits.
- In a subset of participants (n=20) to assess the extent of PRO 140 entry into the genitourinary compartment, and to evaluate virologic responses in genital secretion.

All laboratory reports will be reviewed by the Investigator.

Post-treatment abnormal results that are considered by the Investigator to be clinically significant will be recorded as adverse events. If the Investigator judges it necessary, testing may be repeated in order to make the determination of clinical significance. Validated, quality-controlled laboratory data will be transferred to the main database for analyses.

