### 8.2 DESCRIPTION OF STUDY OUTCOME MEASURES

#### 8.2.1 Primary Safety Outcome Measures

The following metrics will be analyzed to assess the clinical safety of PRO 140 monotherapy regimen:

- Incidence of Treatment-Emergent Adverse Events (TEAE)
- Incidence of Treatment-Emergent Serious Adverse Events
- Incidence of Injection Site Reactions by Investigator evaluation
- Frequency of Grade 3 or 4 adverse events as defined by the DAIDS Adverse Event scale
- Tolerability of repeated subcutaneous administration of PRO 140 as assessed by study participants (using Visual Analogue Scale)
- Changes and shifts in laboratory measurements over time
- Changes in vital signs and weight over time
- Changes and shift in Electrocardiogram (ECG) parameters over time
- Incidence of Physical Examination abnormalities over time

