#### **8.4 RANDOMIZATION AND BLINDING**

All subjects enrolled under this version of the protocol will be randomized in two treatment arms. The study is open label with no blinding requirements.

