### 9.1 ADVERSE EVENT

An adverse event (AE) is defined as any unfavorable or unintended sign, symptom, or disease that occurs or is reported by the subject to have occurred, or a worsening of a pre-existing condition. An AE may or may not be related to the study treatment.

AEs will be elicited through direct questioning and subject reports. Any abnormalities in visit evaluations, physical examination findings or laboratory results that the Investigator believes are clinically significant to the research subject and that occurred after initiation of the first study treatment will be reported as AEs. Abnormal findings that are NOT clinically significant (NCS) should not be recorded as an AE.

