**Table 9-1: DAIDS AE Grading General Guidelines**

Grade	Description
Grade 1	indicates a mild event
Grade 2	indicates a moderate event
Grade 3	indicates a severe event
Grade 4	indicates a potentially life-threatening event
Grade 5	Death related to AE.

DAIDS AE Grading Table Version 2.0- November 2014

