### 9.1.8 SC Injection-related Events

SC and IV injections of concentrated protein materials can be associated with injection-related AEs that impact the ability to safely and successfully deliver the drug. Local injection-site reactions may include pain/discomfort, induration, erythema, nodules/cysts, pruritus, ecchymosis, etc. For SC injections, bleeding, absorption of the drug, leakage of drug, and induration at the local injection site can be additional complications. Other AEs that are common to monoclonal antibody-based therapies are chills, headache, backache, malaise, fever, pruritus, rash, nausea, tingling, and hypertension.

SC injection-related events will be monitored according to the guidelines provided in [Section 17.2](#) (Division of AIDS Table for Grading the Severity of Adult and Pediatric Adverse Events [DAIDS AE Grading Table]). Injection-site reactions thought to be directly related to the injection are considered to be AEs of special interest, and a separate guideline for the acquisition of data related to this AE of special interest is provided in [Section 17.3](#).

For subjects who develop grade 1 event or first occurrence of grade 2 event, continue therapy as per protocol. If a subject chooses to discontinue study treatment, the site should notify the protocol team leadership, and encourage the subject to complete any remaining study visits until the toxicity resolves.

For subjects who develop grade 2 events following study drug injection, the subject should be reevaluated closely until the AE returns to Grade  $\leq 1$ , at which time study treatment may be reintroduced at the discretion of the site Investigator. If the *same* Grade 2 AE recurs following the next administration of study drug, study treatment must be permanently discontinued. Subjects experiencing Grade 3 AEs requiring permanent discontinuation of study treatment should be followed closely for resolution of the AE to Grade  $\leq 2$  and the team leadership must be notified.

Subjects with Grade 3 asymptomatic laboratory abnormalities in cholesterol, creatine kinase (CK) or triglycerides may continue study treatment.

For grade 4 events permanently discontinue therapy.

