8.2.1.4.2 Individual Subject Changes (Shift Tables)

Individual subject changes will be identified through shift tables. Shift tables will be presented for each laboratory parameter with counts and percentages of subjects, for shift (change) from baseline.

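### The Grade 3 or 4 adverse event metric omits severe laboratory values that the open-label investigator judges not significant, and no planned table counts laboratory values by DAIDS grade

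*Protocol*

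**What the plan says.** Protocol 8.2.1 lists nine primary safety outcomes. One is "Frequency of Grade 3 or 4 adverse events as defined by the DAIDS Adverse Event scale"; SAP 3.1.1 repeats it and adds no derivation rule.

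Two rules decide whether a laboratory value can become an adverse event. The closing text of Protocol 7.10 says "Post-treatment abnormal results that are considered by the Investigator to be clinically significant will be recorded as adverse events". Protocol 9.1 gives the converse: "Abnormal findings that are NOT clinically significant (NCS) should not be recorded as an AE". Neither makes an exception for a high grade. Protocol 8.4 adds that "The study is open label with no blinding requirements".

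The SAP handles laboratory data in four places:

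- 8.2.1.4 lists and summarises all available results.
- 8.2.1.4.1 gives raw values and change from baseline for each parameter.
- 8.2.1.4.2 states "Shift tables will be presented for each laboratory parameter with counts and percentages of subjects, for shift (change) from baseline", without saying what the categories are.
- The section on clinically significant abnormalities (numbered 8.2.1.1 a second time) plans a by-subject listing restricted to values judged clinically significant.

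On fatal events, Table 9-1 of the protocol has a Grade 5, "Death related to AE", which the Grade 3 or 4 metric does not name. The same list of primary outcomes includes "Incidence of Treatment-Emergent Serious Adverse Events".

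**The concern.** A reader will take the Grade 3 or 4 frequency as the headline rate of severe toxicity at each dose. For laboratory toxicity, that rate depends on a judgement made by investigators who know the dose, at up to 60 centres, rather than on the measured value and the grading scale. The plan is descriptive (SAP 7.3 and 7.4 rule out inferential statistics), so the tabulated by-dose frequency is itself the result.

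The laboratory summaries would be the natural safeguard, but as specified they do not clearly provide one. Means and changes from baseline can hide a few extreme values. A shift table shows severe abnormality only if its categories are grades. The one dedicated listing of abnormal values uses the same investigator judgement as the metric.

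**Working it through.** No figure in the documents can be reproduced here: neither gives a rate, count or power for this outcome. The check sets the provisions side by side and then gives an illustration on stated assumptions.

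**1. Path of a severe laboratory value judged not clinically significant**

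| Planned output | Does the value appear? | By DAIDS grade? |
|---|---|---|
| Grade 3 or 4 adverse event frequency (Protocol 8.2.1, SAP 3.1.1) | No, under Protocol 7.10 and 9.1 | – |
| Adverse events by severity (SAP 8.2.1.1) | No, it is not an adverse event | – |
| Listings and summaries of all results (SAP 7.2, 8.2.1.4, 8.2.1.4.1) | Yes | No |
| Shift tables (SAP 8.2.1.4.2) | Yes | Not stated |
| Listing of clinically significant values (second SAP 8.2.1.1) | No | – |

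The value stays in the data, but no row commits the SAP to a count of subjects by DAIDS laboratory grade.

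**2. Grading is already within the protocol's scope**

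Exclusion criterion 4 in Protocol 3.3.2 applies DAIDS Grade 4 to laboratory values at entry. Inclusion criteria 10d and 10e in 3.3.1 admit ALT and AST below 5 times the upper limit of normal, so some subjects may start with an abnormal value. Separating existing from emergent abnormality needs baseline grade against worst later grade. Protocol 9.1.8 also anticipates severe values without symptoms: "Subjects with Grade 3 asymptomatic laboratory abnormalities in cholesterol, creatine kinase (CK) or triglycerides may continue study treatment". That sentence concerns continuing treatment, and only cholesterol of its three analytes is in the panel in Protocol 7.10.2, so it is weak support.

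**3. Illustration of size**

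Planned groups, from Protocol section 3 and SAP sections 4 and 5:

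- A: 150 + 75 = 225
- B: 75 + 100 = 175
- C: 100
- Total: 225 + 175 + 100 = 500

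Expected subjects with a Grade 3–4 laboratory value outside the metric = N × (share with such a value) × (share of those judged not significant). Both shares are assumptions.

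| Share with value | Share judged not significant | Of 500 | Of 100 (Group C) |
|---|---|---|---|
| 2% | 25% | 500 × 0.02 × 0.25 = 2.5 | 0.5 |
| 5% | 50% | 500 × 0.05 × 0.50 = 12.5 | 2.5 |
| 10% | 75% | 500 × 0.10 × 0.75 = 37.5 | 7.5 |

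The loss from the metric is smaller wherever the same subject has another Grade 3–4 adverse event.

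**4. Grade 5**

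Read literally, an event graded 5 falls outside a Grade 3 or 4 count. At an assumed fatal-event risk of 0.2% to 1%, that is 500 × 0.002 = 1 to 500 × 0.01 = 5 subjects. Each is still reported: Protocol 9.2 makes any adverse event resulting in death serious, the SAP 8.2.1.1 severity summary has a death category, and Protocol section 12 has the DMC review all deaths.

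**The case against.** The strongest reply is that this is one of nine primary safety outcomes and counts exactly what it names, adverse events. Laboratory toxicity has its own primary outcome, on changes and shifts, which does not depend on the investigator's call. SAP 7.2 excludes no data and SAP 8.2.1.4 lists and summarises everything. Silence on shift categories does not show that DAIDS grades will not be used. No test, power or success criterion depends on the metric.

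Most of this stands, and it limits the point to reporting. It does not supply the missing count: listings across about 500 subjects do not give a by-dose frequency, and undefined categories leave the choice until after the data are seen.

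Three stronger readings are tempting but unsupported:

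- **That severe toxicity is under-counted in the safety report as a whole.** The laboratory values remain in the summaries, shift tables and listings.
- **That deaths are missed.** They are reported in the three places named in step 4. The documents also do not say whether a Grade 4 event that turns fatal overwrites the existing record or opens a new one, so one cannot claim that it drops out of the count.
- **That the rule will create a false difference between doses.** The second and third cohorts are randomised 1:1, and nothing assigns investigators to a dose, so a large gap in flagging by dose would need marked bias among the same assessors. One limited route remains: 150 of Group A's 225 subjects (67%) came from the single-arm cohort, and A and C were never randomised against each other, so drift in judgement over time or between sites could enter pooled summaries. Nothing in the documents shows that it did.

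**Conclusion.** The point holds for this metric and for the missing laboratory table. As worded, the Grade 3 or 4 frequency excludes DAIDS Grade 3–4 laboratory values judged not clinically significant, and no planned output is committed to counting them by grade without that judgement. The by-dose frequency of severe laboratory toxicity therefore rests on an unblinded call.

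The size cannot be derived from the documents. The range of 2.5 to 37.5 subjects in 500 rests wholly on the assumed shares and shows scale only. The omission of Grade 5 is a wording matter. This is a reporting gap worth closing before the tables are programmed; it does not call the trial or its other safety outcomes into question.

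**What to change.** In SAP 8.2.1.4.2:

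- Assign DAIDS grades by program, using the version the protocol cites (2.0), to every laboratory value for which that scale has a grade.
- Define the shift as baseline grade to worst post-baseline grade, by dose group.
- Tabulate subjects with a treatment-emergent Grade 3–4 laboratory value regardless of the clinical-significance call, and place this beside the adverse-event-based frequency.

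As a minor correction in Protocol 8.2.1 and SAP 3.1.1, state the adverse event metric as Grade 3 or higher, so that Grade 5 events are included.

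The cost is one extra programmed table and one changed phrase. Protocol 7.10 already provides for validated laboratory data to be transferred for analysis, so no visit, sample or clinical rule changes. Reported severe-toxicity rates may come out slightly higher.

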### **7.11 PRO 140 ADMINISTRATION**

Refer to [Section 6.4](#) for details.

### **7.12 INJECTION SITE REACTION ASSESSMENT**

[figure not shown]
At each treatment visit that occurs at the clinical site, an injection site reaction assessment will be made for the current and previous injection sites. Injection site reaction assessments are recorded by the Investigator starting after the first injection is given. Refer to [Sections 9.1.8](#) and [17.3](#) for more details.

### 7.13 PAIN ASSESSMENT USING VISUAL ANALOG SCALE (VAS)

Tolerability of repeated subcutaneous administration of PRO 140 is evaluated based on assessment of subject-perceived injection site pain using the Pain Visual Analog Scale (VAS). This assessment will be performed each time subjects arrive to the clinic for the study visit.

Beginning at Treatment Visit 2, subjects will be asked to mark the point that best represents the average pain intensity **over the past week** at the injection site on a horizontal line (100 mm in length) anchored by the following word descriptors at each end, "no pain" on the left side and "pain as bad as it could possibly be" on the right side of the line. The subject marks on the line or by pointing to a position on the line the point that they feel represents their perception of their pain state. The VAS score is determined by measuring in millimeters from the left-hand end of the line to the point that the patient marks.

**Figure 7-1: Visual Analog Scale**

### 7.14 MEASUREMENT OF TREATMENT ADHERENCE

Adherence to assigned regimen during Treatment Phase will be self-reported by subject at T4, T8, T12, T16, and once every four weeks between T18-21, T22-25, T26-29, T30-33, T34-37, T38-41 and T42-45 visits followed by at T48 and VF visits when subject comes to clinic.

## 8 STATISTICAL CONSIDERATIONS

This section presents general information about statistical considerations and concepts such as statistical power, sample size, and a brief discussion on analysis methodology, as well as some data conventions. Detailed descriptions of the statistical analysis methods and data conventions that will be used in this study will be in a separate document; i.e., the Statistical Analysis Plan (SAP).

### 8.1 TREATMENT GROUPS

All eligible subjects in the study will receive PRO 140 as a 350 mg or 525 mg or 700mg subcutaneous injection weekly for up to 48 weeks.

### 8.2 DESCRIPTION OF STUDY OUTCOME MEASURES

#### 8.2.1 Primary Safety Outcome Measures

The following metrics will be analyzed to assess the clinical safety of PRO 140 monotherapy regimen:

- Incidence of Treatment-Emergent Adverse Events (TEAE)
- Incidence of Treatment-Emergent Serious Adverse Events
- Incidence of Injection Site Reactions by Investigator evaluation
- Frequency of Grade 3 or 4 adverse events as defined by the DAIDS Adverse Event scale
- Tolerability of repeated subcutaneous administration of PRO 140 as assessed by study participants (using Visual Analogue Scale)
- Changes and shifts in laboratory measurements over time
- Changes in vital signs and weight over time
- Changes and shift in Electrocardiogram (ECG) parameters over time
- Incidence of Physical Examination abnormalities over time

#### 8.2.2 Primary Efficacy Outcome Measures:

- Proportion of participants experiencing virologic failure at the assigned dose  
*Note: (1) Virologic failure is defined as two (2) consecutive plasma HIV-1 RNA levels of  $\geq$  200 copies/mL. (2) Assigned dose refers to the dose allocated at the time of randomization/enrollment.*
- Time to virologic failure at the assigned dose
- Proportion of participants moved to rescue arm or higher dose group

*Note: Rescue is defined as subjects who were unable to maintain viral suppression, or experienced virologic failure, and moved to a higher dose of PRO 140*

- Proportion of participants achieving viral re-suppression (HIV-1 RNA <50 copies/mL) during Treatment Phase after moving to rescue arm or higher dose group
- Time to achieving viral re-suppression (HIV-1 RNA <50 copies/mL) during Treatment Phase for subjects who moved to rescue arm or higher dose group
- Proportion of participants achieving viral re-suppression (HIV-1 RNA <50 copies/mL) after experiencing virologic failure (during the Treatment and Follow-up Phase)
- Time to achieving viral re-suppression (for virologic failure subjects) after re-initiation of oral combination antiretroviral regimen during the Follow-up Phase.
- Proportion of participants completing 24, 48 weeks of PRO 140 treatment with HIV-1 RNA <50 copies/mL
- Mean change in CD4 cell count, at each visit within the Treatment Phase
- To evaluate the prognostic factors of therapeutic success of PRO 140 monotherapy during the Treatment Phase.
  - a. CCR5 Receptor Occupancy
  - b. CCR5 Genotyping Status
  - c. gp120 genotyping
  - d. Baseline HIV-1 RNA Single Copy levels
  - e. Immune Activation Markers
  - f. PhenoSense® Entry Assay

### 8.2.3 Secondary Exploratory Outcome Measures:

- Measurement of treatment adherence to the PRO 140 monotherapy regimen; this will be assessed using number of missed PRO 140 administrations
- Loss of future drug options

*The first occurrence of intermediate to high level resistance to any one or more of the standard antiretroviral drugs to which the patient's virus was considered to be sensitive at trial entry (i.e. excluding drug resistance present at baseline).*
- Proportion of participants overall and within each treatment group experiencing emerging resistance exhibited by fold increase in maraviroc and PRO 140 FC (Fold Change in IC50 and IC90 relative to wild-type virus) between baseline and the time of virologic failure, as a measure of post-baseline phenotypic resistance

**Note:** *Virologic failure is defined as two (2) consecutive plasma HIV-1 RNA levels of  $\geq 200$  copies/mL.*

**Central Nervous System (CNS) sub-study:** In a subset of participants (n=20):

- Level of HIV-1 RNA in CSF at T1 (prior to first dose of PRO 140), T4 and VF visits
- PRO 140 concentration in CSF at T1 (prior to first dose of PRO 140), T4 and VF visits
- Relationship between PRO 140 concentration in plasma and CSF
- Relationship between PRO 140 concentration in CSF and HIV-1 RNA in CSF
- Relationship between plasma and CSF HIV-1 RNA suppression and HIV disease progression and safety parameters (i.e., adverse events and laboratory abnormalities)

**Genitourinary (GU) sub-study:** In a subset of participants (n=20):

- Level of HIV-1 RNA in genital secretion at T1 (prior to first dose of PRO 140), T4, T16 and VF visits.
- PRO 140 concentration in genital secretion at T1 (prior to first dose of PRO 140), T4, T16 and VF visits.
- Relationship between PRO 140 concentration in plasma and genital secretion
- Relationship between PRO 140 concentration and HIV-1 RNA in genital secretion,
- Relationship between plasma and genital secretion HIV-1 RNA suppression and HIV disease progression and safety parameters (i.e., adverse events and laboratory abnormalities)

#### **8.2.4 Safety Assessments**

Safety measurements will include:

- Tolerability of repeated subcutaneous administration of PRO 140 as assessed by study participants (using Visual Analogue Scale) and by Investigator-evaluation of injection site reactions.
- Frequency of Grade 3 or 4 adverse events as defined by the DAIDS Adverse Event scale
- Frequency of treatment-emergent serious adverse events

#### **8.3 SAMPLE SIZE DETERMINATION AND RATIONALE**

Three hundred (300) subjects will be enrolled in this study. The sample size is selected on the basis of clinical judgment.

#### **8.4 RANDOMIZATION AND BLINDING**

All subjects enrolled under this version of the protocol will be randomized in two treatment arms. The study is open label with no blinding requirements.

## 8.5 INTERIM ANALYSIS

The interim analysis will be directed and conducted by an independent DMC, which will include clinicians with expertise in HIV disease, a neurologist or psychiatrist and at least one biostatistician who is not otherwise involved in the trial. The iDMC will monitor the safety of the trial from the beginning and at approximately six month intervals based on enrollment thereafter. The main purpose of this IA is to ensure the safety of the subjects in the trial and to recommend whether the trial should be stopped early to protect the safety of the participants.

The iDMC will closely monitor the following:

- Virologic failure and viral re-suppression (after oral combination therapy is re-instituted).
- Long-term safety follow-up data for one year after completion of treatment phase
- In addition to other safety parameters, all baseline/post-treatment tropism, resistance, prognostic factors such as, HIV-1 RNA single copy assay, immune activation markers etc. and any potential cardiovascular events (that may occur from inflammatory bursts post-drug withdrawal)

A detailed interim analysis plan will be prepared and presented to the DMC prior to the conduct of the interim analysis.

The details of the IA, including the below bullet points, will be included in the Statistical Analysis Plan (SAP) for the study.

- The goals of the IA
- IA procedures for data preparation
- IA procedures conduct of the analysis
- Futility analysis and stopping rule
- Data to be shared with the DMC
- Information to be shared with the sponsor after the IA

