PRO 140 525mg	Parenteral solution	175 mg/mL	2 injections of PRO 140 (2 X 1.5 mL/inj.) for remainder of treatment phase	SC injection										
PRO 140 700mg	Parenteral solution	175 mg/mL	2 injections of PRO 140 (2 X 2 mL/inj.) for remainder of treatment phase	SC injection										

Name of Sponsor: CytoDyn, Inc.	
Name of Study Product: PRO 140 (Humanized monoclonal antibody to CCR5)	
Protocol Number: PRO 140_CD03	Indication: Human Immunodeficiency Virus Type-1 (HIV-1) Infection
of physical examinations, as detailed in the schedule of procedures and assessments of the protocol.	
Follow-up Phase: Duration of Follow-up Phase is determined based on whether or not subject has experienced virologic failure during the Treatment Phase. 
 
Group A or Group B subjects not participating in Part 2 and Group C subjects who experience virologic failure during the Treatment Phase will be assessed every 4 weeks until the viral suppression is achieved (i.e., plasma HIV-1 RNA levels decline to < 50 copies/mL). Additionally, virologic failure subjects will return to clinic for long-term follow-up at 6 months and at one year from the time of the Virologic Failure (VF) Visit.
 
Subjects who do not experience virologic failure and complete Treatment Visit 48 (T48), will be assessed every 2 weeks for total of 4 weeks.
 
	
Duration of Treatment: 
 
Screening Phase: up to 6 weeks
 
Treatment Phase: 48 weeks ± allowed windows (up to 48 treatments every week (±3 days)).
 
Follow-up Phase: 
 
Virologic Failure: Until viral suppression is achieved. Additionally, subjects who experience virologic failure will return to clinic for long-term follow-up at 6 months and at one year from the time of the Virologic Failure Visit.
 
Non-Virologic Failure (NVF): 4 weeks
 
 
 
	
Total Study Duration: 58 weeks [Does not include additional long-term follow-up time for virologic failure subjects]	

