#### 4.4 FOLLOW-UP PHASE

The duration of follow-up depends on whether subject experiences virologic failure.

- Subjects who experience virologic failure within the Treatment Phase will be assessed every 4 weeks until viral suppression is achieved (i.e., plasma HIV-1 RNA levels decline to < 50 copies/mL). Additionally, virologic failure subjects will return to clinic for long-term follow-up at 6 months and at one year from the time of the Virologic Failure (VF) Visit.

- Subjects who do not experience virologic failure at the end of the Treatment Phase, will be assessed every 2 weeks for total of 4 weeks.

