#### 4.4.1.2 Long-Term Follow-Up Visits

Additionally, subjects who experience virologic failure will also return to clinic for the long-term follow-up at 6 months and at one year from the time of the Virologic Failure Visit.

The following assessments will be performed at VF-6mFU and VF-12mFU visit, unless otherwise specified:

- Assess for any Adverse Events and changes in combination antiretroviral therapy (see [Section 9](#) and [7.5](#))
  - **Note:** *Only SAEs and any AE that is considered possibly or probably or definitely related to the study treatment by the Investigator will be captured during the long-term follow-up phase.*
- Collection of Blood Specimens (see [Section 7.10](#)) for
  - Plasma HIV-1 RNA level
  - TruCount T Assay
  - HIV Drug Resistance Assay (GenoSure Prime or PhenoSense GT/Integrase)
  - HIV Trofile® DNA or RNA Assay
  - HIV PhenoSense Entry® Assay

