## 5 SUBJECT COMPLETION AND WITHDRAWAL

### 5.1 SUBJECT COMPLETION

- A subject who completes the 48-week Treatment Phase and 4-week Non-Virologic Failure Follow-Up Phase will be considered as having completed the study.
- A subject who experiences virologic failure during the 48-week Treatment Phase, and undergoes the Virologic Failure (VF) Visit assessments and is followed up until viral suppression is achieved and complete Virologic Failure – 12 month Follow-Up (VF-12mFU) Visit, will be considered as having completed the study.

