#### 9.1.1 Reporting of Adverse Events

Report initiation for all AEs and SAEs will begin at the time of the first treatment visit and continue up until the final study visit (i.e. up to NVF-FU2 for subject who do not experience virologic failure or until viral suppression is achieved for subjects who experience virologic failure). Additionally, virologic failure subjects will have a long-term follow-up visits at 6 months and at one year from the time of the Virologic Failure Visit. Only SAEs and any AE that is considered possibly or probably or definitely related to the study treatment by the Investigator will be captured during the Long-term Follow-up Phase of the study. All events will be followed to resolution or until 30 days after the subject completes the study. A final assessment of outcome will be made at that time.

All AEs must be recorded in the subject's medical records and on the eCRFs. AEs will be reported using customary medical terminology along with the following information: the onset and end dates, whether the event is considered to be a SAE (see [Section 9.2](#)), the impact the event had on study treatment (see [Section 9.1.2](#)), the DAIDS AE grade (intensity) of the event (see [Section 9.1.3](#)), the causality of the event (see [Section 9.1.4](#)), whether treatment was given as a result of the event (see [Section 9.1.5](#)), and the outcome of the event (see [Section 9.1.6](#)).

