2.3 Study Duration

- **Screening Phase:** up to 6 weeks
- **Treatment Phase:** 48 weeks ± allowed windows (up to 48 treatments every week (±3 days)).
- **Follow-up Phase:**
 - Virologic Failure: until viral suppression is achieved. Additionally, subjects who experience virologic failure will return to clinic for long-term follow-up at 6 months and at one year from the time of the Virologic Failure Visit.
 - Non-Virologic Failure (NVF): 4 weeks

Total Study Duration will be 58 weeks, which does not include additional follow-up time for virologic failure subjects.

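### The DMC is to monitor safety for one year after treatment, but subjects without virologic failure are followed for only 4 weeks after T48

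*Protocol*

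**What the plan says.** **What the DMC is to monitor.** The Synopsis (Interim Analysis) and Protocol 8.5 both list "Long-term safety follow-up data for one year after completion of treatment phase" among the items for close monitoring. Neither names a subgroup. The next item on the list includes cardiovascular events that might follow inflammatory bursts after drug withdrawal.

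**Subjects without virologic failure.** The Synopsis gives "Non-Virologic Failure (NVF): 4 weeks". Protocol 4.4 says they "will be assessed every 2 weeks for total of 4 weeks", and Table 4-3(a) shows two visits, at 2 and 4 weeks after T48. Protocol 5.1 then closes their participation: "A subject who completes the 48-week Treatment Phase and 4-week Non-Virologic Failure Follow-Up Phase will be considered as having completed the study". Under Protocol 9.1.1, AE and SAE reporting runs "up to NVF-FU2 for subject who do not experience virologic failure".

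**Subjects with virologic failure.** Protocol 4.4.1.2 adds "long-term follow-up at 6 months and at one year from the time of the Virologic Failure Visit". At these visits only SAEs and AEs considered possibly, probably or definitely related are captured (Table 4-3(b), 4.4.1.2, 9.1.1). SAP 8.1.5 likewise ties the long-term safety visits to virologic failures.

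**TEAEs.** SAP 8.2.1.1 defines a TEAE by onset on or after first treatment and gives no end date.

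**The concern.** The DMC item describes post-treatment safety data that the schedule does not collect for one class of subject. Two things are at stake.

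- **What the DMC can see.** Part of its stated remit cannot be met for subjects without virologic failure. The withdrawal-related cardiovascular item shows why this matters: a new event in such a subject more than 4 weeks after T48 falls outside scheduled collection. Table 4-3 schedules neither an ECG nor immune activation markers in follow-up for anyone.
- **How the safety tables read.** Because the TEAE definition is open-ended, events from the 6- and 12-month visits would enter the same incidence figures as events from subjects observed to 4 weeks. The later events would come only from virologic failures and only from a restricted set of event types.

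**Working it through.** **1. Reproduce the plan's own duration.** The inputs are screening up to 6 weeks, treatment "48 weeks ± allowed windows" (SAP 2.3), and 4 weeks of follow-up without virologic failure.

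6 + 48 + 4 = 58 weeks

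This is exactly the stated total study duration, which the Synopsis says leaves out the long-term follow-up of virologic failures. No longer phase for the other subjects is hidden in it.

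**2. What the DMC item would need if read as written.** Taking one year as 52 weeks:

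6 + 48 + 52 = 106 weeks per subject

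The shortfall for a subject without virologic failure is 52 − 4 = 48 weeks. Such a subject has 4/52, or about 8%, of the stated period.

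**3. What each kind of subject has.**

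| Subject | Scheduled follow-up after PRO 140 | Start point |
|---|---|---|
| Completes T48, no failure | 4 weeks | T48 |
| Stops for a reason other than failure | T48 assessments, then Follow-up Phase; no one-year visit scheduled (Protocol 4.2, Note) | T48 assessments |
| Fails and leaves treatment at the VF Visit | 6 and 12 months (±1 month), so about 52 weeks after own treatment ended | VF Visit |
| Fails and enters Part 2 | Not clearly stated (step 5) | Unclear |

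**4. How many subjects have 4 weeks only.** With v the share with virologic failure and 500 planned subjects, the number is 500 × (1 − v). The documents give no projected v, so it is an assumption here:

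- v = 30%: 500 × 0.70 = 350
- v = 50%: 500 × 0.50 = 250
- v = 70%: 500 × 0.30 = 150

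**5. Part 2 subjects.** The relevant passages, side by side:

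- The Synopsis (Follow-up Phase) gives 4-weekly follow-up to Group A or B failures not taking part in Part 2 and to Group C failures. It gives the 4-week track to subjects who complete T48 without failing. A rescued subject who reaches T48 without a second failure fits neither description.
- Protocol 4 and 4.4 speak more broadly of subjects who fail during the Treatment Phase, which could include that same subject.
- The Synopsis (Treatment Phase) and Protocol 4.2 say a Part 2 subject who fails again has VF Visit assessments and then enters follow-up. Protocol 4.3 places the VF Visit assessments before entry to follow-up.
- None of these says whether a first or a second VF Visit starts the 12 months.

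**The case against.** The strongest reply is that this is only a missing qualifier. The Protocol uses the term long-term follow-up for virologic failures throughout, and SAP 8.1.5 uses almost the same phrase for failures alone. Failures who do not enter Part 2 leave the Treatment Phase at the VF Visit, so for them the DMC item is accurate. Protocol 12 ties the DMC's review to events in the Treatment and Follow-up Phases, which is the schedule as written. Subjects without failure restart antiretroviral therapy one week before treatment ends, so no interval without therapy is planned for them. One-year safety is not a listed outcome, so no endpoint, estimate or sample size changes.

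Most of this stands, and it limits the point to a correction of wording and presentation. It does not remove it. The item names no subgroup and counts from completion of the treatment phase, not from the VF Visit. The DMC charter and the detailed interim plan might add the qualifier, but they are not in the documents. Protocol 8.5 says the SAP will cover the data shared with the DMC, and the SAP as supplied has no interim analysis section. Existing events are followed further (9.1.1, 9.2.2), but that does not collect new ones.

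A reader might go further and infer that the stated follow-up is missing for most subjects. That requires a failure share below 50%, and the documents do not settle it:

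- In the earlier 12-week study at 350 mg, 20 of 43 (46.5%; exact 95% CI 31% to 62%) did not complete free of failure.
- Adding one failure before the extension and five during it gives at most 26 of 43 (60.5%; 44% to 75%). This assumes that all 20 failed and includes failures after 48 weeks. Those studies used a threshold of 400 copies/mL.
- Protocol 1.5 says a majority failed in the extension, while 1.4.2.8 reports 5 of 16 eligible subjects.

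**Conclusion.** The inconsistency is real and rests on the text alone. No subject without virologic failure has scheduled follow-up, or collection of new AEs and SAEs, beyond 4 weeks after T48, although the DMC item states one year for all. The gap is 48 weeks for each such subject. How many subjects it affects depends on the assumed failure share: 350, 250 or 150 of 500 at 30%, 50% or 70%. All scheduled safety data at 6 and 12 months come from virologic failures and cover a restricted set of events.

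A reader might also infer that the long-term data of rescued subjects are partly on-treatment. That follows only if the first VF Visit starts the clock. With T*k* on day 1 + 7(*k* − 1), failure at T12 is day 78 and T48 is day 330. The 6-month visit would then be day 78 + 182 = 260, which is 10 weeks before T48. The 12-month visit would be day 78 + 365 = 443, about 16 weeks after T48. The documents leave the start point open, so this shows why they need to be clear; it is not a finding about the data.

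The correction should be made before DMC and final safety tables are produced. It does not affect any efficacy result.

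**What to change.** 1. In the Synopsis and Protocol 8.5, replace the DMC item with what is collected: for virologic failures, SAEs and related AEs at 6 and 12 months from the VF Visit; for all other subjects, safety data to 4 weeks after T48.
2. In DMC and final safety tables, show long-term events separately, labelled *virologic failures only*, and do not pool them into TEAE incidence. SAP 8.2.1.1 needs a sentence saying so.
3. Reconcile the passages on Part 2 subjects (Synopsis, Treatment Phase and Follow-up Phase; Protocol 4, 4.2, 4.3 and 4.4), so that they state which VF Visit starts the 12 months and which follow-up track applies to a rescued subject who reaches T48 without a second failure. This review does not propose the answer. It is a schedule decision, not only wording: in the T12 example, counting from T48 instead of the first VF Visit would move the last visit from day 443 to day 330 + 365 = 695, or 36 weeks later.

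Items 1 and 2 cost a protocol wording change in two places, one SAP sentence and one extra table. They add no visits, and the 58 weeks do not change. The stated follow-up becomes less favourable, but it then matches what is collected.
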